8.0 Study Withdrawal/Discontinuation

Reasons for Withdrawal

A study subject will be discontinued from participation in the study if any of the following occur:

- Inability of study personnel to contact subjects for follow-up vaccinations
- Excessive appointment cancellations (> 6) by the subject
- Subject withdrawals consent to continue in the research for any reason
- An unanticipated/unacceptable toxicity or adverse event (AE)

Handling of Withdrawals

There is minimal risk involved in this study. As the intervention under investigation is a reduced schedule of a currently used vaccine, patients who choose to withdraw will not be under any additional risk beyond that of normal patient care. Patients who choose to withdraw will not be contacted any further after notifying study staff. However, the data that they have provided up to the point of withdrawal will be retained and possibly used for research purposes.

Termination of Study

This is a minimal risk study with no foreseeable reasons for potential termination.

9.0 Statistical Considerations

Data Analysis: We will compare the immunogenicity of the 2-dose experimental group to the 3-dose standard care group for the corresponding sex. Participants will be required to 1) have received all injections of the vaccine within the predetermined time ranges, 2) have an adequate serum sample collected at the appropriate time intervals, and 3) be seronegative at T_0 for the HPV type that will be analyzed. Results of this experiment will be analyzed using intention-to-treat analyses, as these are the standard for non-inferiority trials.

Aim 1. Determine if a 2-dose schedule of the HPV vaccine administered at 0 and 6 months to females 15–26 years old elicits a non-inferior type-specific antibody response to that generated in females 15–26 years old who receive the currently recommended 3-dose schedule.

H_a : Two-dose 9-valent HPV vaccination immunogenicity levels among females are non-inferior to 3-dose 9-valent HPV vaccination immunogenicity levels among females.

H_0 : Two-dose 9-valent HPV vaccination immunogenicity levels are inferior to 3-dose 9-valent HPV vaccination immunogenicity levels among females.

Non-inferiority of antibody GMTs at 1 month after the last dose is administered will be tested by developing 2-sided 95% confidence intervals for the ratio of GMTs drawn at T₃, as is consistent with the power analyses of non-inferiority trials in the literature.⁸ This will be equivalent to the lower bound of a 1-sided 97.5% confidence interval (1-sided test, $\alpha=0.025$). The ratio will be developed using antibody GMTs in 15–26 year old females in the 2-dose study group relative to antibody GMTs among 16–26-year-old females in the 3-dose standard care group. In order to reject the null hypothesis, the lower bound of the ratio of antibody GMTs in females who received 2 doses should be 0.5 or greater for each of the 9 vaccine types.¹⁷⁻²⁶ If inferior immunogenicity is noted for any of the 9 vaccine types for the 2-dose experimental group, then H₀ will not be rejected.

Aim 2. Determine if a 2-dose schedule of the HPV vaccine administered at 0 and 6 month to males 15–26 years old elicits a non-inferior type-specific antibody response to that generated in males 15–26 years old who receive the currently recommended 3-dose schedule.

H_a: Two-dose Gardasil 9 immunogenicity levels among males are non-inferior to 3-dose 9-valent HPV vaccine immunogenicity levels among males.

H₀: Two-dose Gardasil 9 immunogenicity levels among males are inferior to 3-dose 9-valent HPV vaccine immunogenicity levels among males.

Non-inferiority of antibody GMTs at 1 month after the last dose is administered will be tested similar to the analysis plan presented for Aim 1. Two-sided 95% confidence intervals for the ratio of antibody GMTs drawn at T₃ will be developed. The ratio will consist of antibody

GMTs in 15–26-year-old males as compared to 15–26-year-old males in the 3-dose standard care group. In order to reject the null hypothesis, the lower bound of the 95% confidence interval for the ratio of antibody GMTs in males should be 0.5 or greater for each of the 9 vaccine-type HPVs. If inferior immunogenicity is noted for any of the 9 vaccine types, then H₀ will not be rejected.

Secondary analyses: We will also compare immunogenicity of the experimental 2-dose group in males with the immunogenicity of the 3-dose standard care group in females. This will allow us to compare the immunogenicity of the 2-dose schedule in males to that of the standard schedule in females, the population originally studied in efficacy trials.^{14,15} Non-inferiority at T₃ will be tested by constructing 2-sided 95% confidence intervals for the ratio of antibody GMTs among the 2-dose 15–26-year-old male experimental group as compared to the 3-dose 15–26-year-old female group. To determine non-inferiority between the 2 groups, the lower bound of the ratio of antibody GMTs in males should be 0.5 or greater for each of the 9 vaccine types. We will also determine whether the level of immunogenicity for each type is above naturally-acquired immunity among males at T₃.

Aim 3: Evaluate the persistence of the immune response by comparing antibody levels 6 months after the last dose in (a) females 15–26 years of age receiving 2 vs 3 doses and (b) males 15–26 years of age receiving 2 vs 3 doses.

H_a: Two-dose Gardasil 9 immunogenicity levels are non-inferior to 3-dose 9-valent HPV vaccine immunogenicity among females and males at 6 months after the last dose.

H₀: Two-dose Gardasil 9 immunogenicity levels are inferior to 3-dose 9-valent HPV vaccine immunogenicity among females and males at 6 months after the last dose.

Non-inferiority of antibody GMTs at 6 months after T₂ will be tested by constructing two-sided 95% confidence intervals for the ratio of antibody GMTs drawn at T₄. The ratios will consist of antibody GMTs in 15–26-year-old females in the 2-dose group as compared to 15–26-year-old females in the 3-dose standard care group. Likewise, ratios of antibody GMTs in 15–26-year-old males in the 2-dose experimental group as compared to 15–26-year-old males in the 3-dose standard care group will be constructed. In order to reject the null hypothesis, the lower bound of the 95% confidence interval for the ratio of antibody GMTs in both comparisons should be 0.5 or greater for each of the Gardasil 9 types. If inferior immunogenicity is noted for any HPV type for either sex, then H₀ will not be rejected.

Sample Size Justification:

The sample size determined for this study takes into account the need to recruit a sufficient number of participants who 1) could be included in assessments for the 9 HPV types that the vaccine protects against, considering that some may have been exposed before baseline, and 2) to account for loss to follow-up. Power analysis calculations were performed using estimates from published clinical trials and HPV prevalence rates in the age groups that will be included in this study. It was estimated that up to 15% of study participants will be seropositive for 1 or more vaccine types.¹⁶ We then assumed an attrition rate of 15% at the 12-month follow-up point.

We calculated the sample size for the hypothesis: H_a: Antibody response to 2 doses will be non-inferior to the antibody response to 3 doses of Gardasil 9 for females (Aim 1) and males (Aim 2). The GMTs will be non-inferior if the true ratio between each study group (female 2-dose and male 2-dose) and the 3-dose standard care groups (female 3-dose and male 3-dose) are equal to 1.2, with a standard deviation of 1.2 consistent with the power analyses conducted by a previous clinical trial.⁸ The inferiority margin was set at 0.5, which is the standard in HPV vaccine clinical trials¹⁷⁻²⁶. The statistical criterion for non-inferiority will be determined to be null when the lower bound of the 97.5% confidence interval for the GMT is 0.5 or greater for any of the vaccine types. A sample size of 91 in each group who are naïve to at least 1 of the vaccine types is required to reach 90% power to detect non-inferiority of the 2-dose compared to the 3-dose regimen at T₃. Based on estimates of 15% of the baseline samples testing seropositive for at least one of the types, a sample size of 108 is required in each group for comparisons of T₃ antibody titers.

We also calculated the sample size for the hypothesis: H_a: Two-dose 9-valent HPV vaccine immunogenicity levels are non-inferior to 3-dose Gardasil 9 immunogenicity among females and males at 6 months after the last dose. Between T₀ and T₄, we assumed an attrition rate of 15%. Therefore, each comparison group requires a total sample size of 128 per group to achieve at least 90% power to determine non-inferiority of the 2-dose experimental groups compared to the 3-dose standard care groups at T₄. The total sample size required is 800. All calculations were made using statistical software PASS, version 15.

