5.0 Study Procedures

Baseline visit:

Project staff will follow standardized instructions to ensure unbiased and systematic data collection. At the baseline visit, all participants will have their blood drawn (B₁; see Figure 1), which will be processed and later sent to the CDC lab to determine their baseline levels of antibodies for the 9-valent HPV types. After the blood draw, participants will be randomized to either the 3-dose standard care group or the 2-dose experimental group. All participants will receive the first dose of the HPV vaccine (V₁) at this time (T₀). They will be observed for up to 15 minutes after the injection to ensure they do not have any adverse reactions to the vaccine. Participants will be scheduled for their next visit before leaving the clinic.

Demographics (i.e., date of birth, age, ethnicity, race, marital status) and other information (i.e., height, weight, coverage, and clinic site) will be collected by project staff (via the EMR and subjects’ self-reports) utilizing internal-use documents previously approved by the IRB.

An appointment reminder handout will be distributed to all subjects. It will specify when they are scheduled to receive follow up doses and state that they are in a clinical trial and thus should not receive the HPV vaccine at a regular clinic visit.

Follow-up visits:

Participants will be screened during each follow-up vaccination visit to ensure they continue to meet those inclusion and exclusion criteria required for safe vaccination, including whether they have developed any new allergies to the vaccine's components. Febrile patients or those who received another vaccine will be rescheduled, if possible, to do so within the allowed window for vaccination (± 4 weeks). Study personnel may call participants who miss a scheduled visit (due to transportation issues or scheduling conflicts) prior to withdrawing them from the study. These participants will be offered a home visit to receive the time-sensitive follow up study procedure (i.e., vaccination, urine pregnancy test, or blood draw) that they need to stay within their allowed window and remain in the study.

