Participants will also be screened to determine if they received the vaccine at another location. Those who receive HPV vaccination doses outside the study or do not meet the study parameters will be excluded. In an effort to prevent doses being administered by clinic personnel outside of the study, the project manager will post notices at the clinic prompting nurses to check the FYI flags in EPIC and/or will attend one or more of the clinics' in-service events to remind them in person. Which option to be utilized will be determined by each clinic manager's preference.

Participants who are pregnant when their follow-up visit window closes will be removed from the study.

At T_1 , only participants in the standard 3-dose arm of the study will need to return to the clinic. Two months ± 4 weeks after T_0 , 3-dose arm participants will receive a second dose of the HPV vaccine (V_2) (Figure 1). The window of time for vaccination is similar to that used in the 2-dose study in 9–14 year olds by Iversen et al.⁸ Participants in the experimental group will not receive a vaccine dose at 2 months and therefore will not need to attend clinic at T_1 .

Six months after enrollment (T_2), the third dose of Gardasil 9 (V_3) will be administered to the standard 3-dose group and the second dose (V_2) will be administered to the experimental 2-dose group. Participants will have a window of 6 months ± 4 weeks after T_0 to receive their final dose

The second blood (B_2) draw will be done at T_3 , which will be timed to 3–7 weeks after T_2 when the final HPV dose was administered. The third and final blood draw (B_3) will be done at T_4 , 6 months ± 4 weeks after T_2 . Participants will be reimbursed for their time and effort at the time of each blood draw: \$50 for B_1 and B_2 and \$75 for B_3 . After the B_3 blood draw, we will administer the 3rd dose to participants in the 2-dose arm with their consent.

We considered collecting blood specimens at more or less frequent intervals. Timing of collection of blood specimens was carefully considered, and we chose a sampling scheme that would limit the number of blood draws while still allowing us to achieve the aims of the study. We also considered collecting all information via self-report, such as vaccination history. However, the literature demonstrates that patients often forget whether they were vaccinated, and therefore, accessing past vaccination records to improve reliability of vaccination history is necessary.

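### Section 9.0 gives two incompatible primary populations, and its reason for intention-to-treat is wrong for a non-inferiority trial

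*Combined protocol and SAP*

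**What the plan says.** The Data Analysis paragraph of section 9.0 sets three conditions for being analysed. Participants must "have received all injections of the vaccine within the predetermined time ranges", must "have an adequate serum sample collected at the appropriate time intervals", and must "be seronegative at T_0 for the HPV type that will be analyzed". The sentence that follows reads: "Results of this experiment will be analyzed using intention-to-treat analyses, as these are the standard for non-inferiority trials".

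Section 5.0 (Follow-up visits) adds rules that take participants out after randomisation:

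- Staff may telephone those who miss a visit "prior to withdrawing them from the study", and a home visit is offered.
- "Those who receive HPV vaccination doses outside the study or do not meet the study parameters will be excluded".
- "Participants who are pregnant when their follow-up visit window closes will be removed from the study".

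The T3 blood draw is tied to the last dose, "which will be timed to 3–7 weeks after T_2 when the final HPV dose was administered".

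The sample-size text in section 9.0 starts from 91 per group, raises this to 108 for baseline seropositivity of 15%, and then to 128 for attrition of 15%.

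The document does not define an intention-to-treat set, say which set is primary, plan an analysis in a second population, or say how a missing T3 or T4 titre would be handled.

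**The concern.** Baseline seronegativity is fixed before randomisation, so it can be combined with analysis by assigned arm. The other two conditions arise after randomisation. Restricting to participants who complied with dosing and sampling is a per-protocol analysis, and calling the result intention-to-treat contradicts it.

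The justification is a second fault. In a superiority trial, intention-to-treat tends to be conservative because deviations dilute a difference. In a non-inferiority trial the same dilution can hide a real deficit. This design offers a direct route: a 3-dose participant who misses only the 2-month dose has in effect received the 0- and 6-month schedule under test.

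The per-protocol set has its own weakness. It depends on post-randomisation exclusions, and no planned analysis checks their effect. With the primary set left open, the population could be chosen after the titres are known, and this applies to Aims 1, 2 and 3 alike.

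**Working it through.** **1. Which population do the other sections fit?**

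- Sample-size chain: 91 / 0.85 = 107.1, rounded up to 108; 108 / 0.85 = 127.1, rounded up to 128. Both steps reproduce. They treat seropositive and lost participants as not analysed. That fits the restricted set and does not fit an analysis of everyone randomised, although it does not by itself show that dosing compliance was meant to be required.
- The 91 does not reproduce from the stated inputs. With margin ln 2, true ratio 1.2, SD 1.2 (natural log assumed, since the scale is not stated), one-sided alpha 0.025 and 90% power, n = 2 × 1.2² × (1.960 + 1.282)² / (ln 2.4)² ≈ 39.5, or 40 per group. This is a separate matter, and nothing below depends on it.
- The section 5.0 exclusions and withdrawals also fit the restricted set.

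**2. Which way could a literal intention-to-treat analysis err?** No deviation rate is given in the document, so the rates below are assumptions.

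Inputs from section 9.0: margin 0.5, SD 1.2, one-sided alpha 0.025. Group size: 91 (the plan's figure) or 144, from 800 / 4 = 200 and 200 × 0.85 × 0.85 = 144.5. The 144 assumes that the 800 split equally over the four sex-by-arm groups.

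Suppose the true ratio is 0.5 and a fraction f of the 3-dose arm responds like the 2-dose arm. Then:

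- observed ratio = 0.5^(1 − f), a shift of f × ln 2 on the log scale
- SE = 1.2 × √(2/n), which is 0.1779 at n = 91 and 0.1414 at n = 144
- per-type error = 1 − Φ(1.96 − f × 0.693 / SE)

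| f (assumed) | Observed ratio | Error, n = 91 | Error, n = 144 |
|---|---|---|---|
| 0 | 0.500 | 2.5% | 2.5% |
| 5% | 0.518 | 3.9% | 4.3% |
| 10% | 0.536 | 5.8% | 7.1% |
| 20% | 0.574 | 11.9% | 16.4% |

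Example for f = 10%, n = 144: 0.0693 / 0.1414 = 0.49, and 1 − Φ(1.47) = 0.071.

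**3. Can the direction reverse?** Yes. Suppose instead that 10% of the 2-dose arm lack the second dose and have half the 2-dose GMT (assumed). The ratio becomes 0.5 × 0.5^0.1 = 0.467, and the error at n = 91 falls to 1 − Φ(1.96 + 0.39) = 0.9%.

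**4. Does it matter at the planning ratio?** Hardly. At a true ratio of 1.2, 10% dilution gives 1.2^0.9 = 1.18. Per-type power at n = 91 moves from 99.85% to 99.79%.

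**The case against.** The best defence is that the intended population can be recovered. The three conditions, the exclusions in section 5.0 and the sample-size chain all point to a type-specific evaluable set. A single sentence says otherwise, and it may mean only that participants are kept in their assigned arm within that set. This is a fair reading, and it supports the direction of the fix. But the text does not say so, and the rationale attached to the sentence would still be wrong.

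A reader might also infer more than the document supports:

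- *That intention-to-treat always favours non-inferiority here.* It does not; step 3 shows a reversal. The diluting direction is the more plausible one, because the 3-dose arm has one more dose to miss, and because T3 is timed from the final dose, so a 2-dose participant without a second dose would normally have no T3 sample. Plausibility does not justify a flat claim.
- *That errors of 7% or 16% are to be expected.* The missed-dose rates are assumed, and telephone calls, home visits and windows of ± 4 weeks are there to limit them. If the removal rules are applied strictly, most deviators would give no T3 serum. The scenario in step 2 would then largely not arise, and a literal intention-to-treat analysis would need a missing-data method that the plan does not give.
- *That the extra visit and, for females, the extra pregnancy test in the 3-dose arm bias the per-protocol result.* They create more opportunities for exclusion in that arm, but the document gives no rate and no link between exclusion and titre.

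**Conclusion.** The point stands as an error in the text. Two adjacent sentences define incompatible primary populations for Aims 1–3, and the reason given for intention-to-treat is unsound for non-inferiority. Neither conclusion depends on a calculation.

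The numerical consequence is conditional. It is a risk when the true ratio for a type is near 0.5 and deviations make the arms alike. With 10% of the 3-dose arm assumed to be in effect on the 2-dose schedule, the per-type one-sided error is about 6–7% instead of 2.5% (n = 91 to 144, natural-log SD 1.2). Every one of the nine types must pass, so the error for an aim cannot exceed the per-type figure and may be lower. The document does not show that the conclusion of each aim would turn on which sentence is followed; at the assumed ratio of 1.2 the choice makes almost no difference.

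What remains under either reading is that no planned analysis tests whether the post-randomisation exclusions affect the result.

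**What to change.** In section 9.0:

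1. Delete the intention-to-treat sentence together with its rationale.
2. Name the type-specific per-protocol set (doses in window, adequate and timely serum, seronegative at T0 for that type), analysed by assigned arm, as primary for Aims 1–3.
3. Add a supportive analysis, by assigned arm, of all randomised participants who are seronegative at T0 for the type and have a T3 titre (T4 for Aim 3), regardless of dose, window or outside-vaccination deviations.
4. Report both analyses, give exclusions by arm and reason, and discuss any difference in conclusion.

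The withdrawal, exclusion and removal rules in section 5.0 should be reconciled with the populations that section 9.0 then names.

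The cost is a wording change and one extra analysis. No larger sample is needed on this account: about 144 per group under the equal-split assumption exceeds the plan's 91. The limitation is that the supportive set can include only titres that are actually collected, so strict use of the removal rules would leave it little larger than the primary set.

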For those who agree to participate and meet all inclusion and exclusion criteria, written informed consent will be obtained. For those <18 years of age, a parent/guardian will provide written consent and the adolescent will provide written assent. Screening and recruiting procedures will occur in a private space whenever available. We will devote adequate time to explain the study to participants and parents of minors using terminology they can understand in English or Spanish, when needed. Potential participants who do not meet study criteria will be directed to their physician or a facility that can provide the HPV vaccine to them. To increase efficiency and decrease patient burden, the patient record numbers of those who decline will be recorded so that they are not approached again in future visits.

To clarify, a) permission to contact patients to participate was obtained from their individual providers and b) a waiver of consent was requested in order to pre-review patient medical records for eligibility to participate in this study.

Randomization:

After obtaining informed consent, enrolled participants will be randomized in a 1:1 ratio to either the 2-dose study group or the 3-dose standard care group. The UTMB Office of Biostatistics

(OBIOS) will generate the randomization scheme. The scheme will be centralized on a secure website to facilitate access to study personnel and eliminate selection bias. At the time that a participant has signed informed consent and met all eligibility criteria, study personnel will utilize REDCap, which has been programmed to randomize patients as described above, to obtain the study allocation information. Study personnel will be required to enter information including the protocol number, the site number, and participant’s age and sex to receive the participant identification number and study assignment for the 2-dose study group or the 3-dose standard care group. The PI has previously used these techniques in randomized trials conducted in UTMB clinics with excellent success.

[figure not shown]

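### No covariate is named for any GMT ratio: a modest loss of precision in the randomised aims, and an unprotected, non-randomised comparison of 2-dose males with 3-dose females

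*Combined protocol and SAP*

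**What the plan says.** For Aim 1, section 9.0 states that non-inferiority at T3 "will be tested by developing 2-sided 95% confidence intervals for the ratio of GMTs". Aim 2 follows the same approach for males, and Aim 3 repeats it at T4 for each sex. Every type must have a lower limit of at least 0.5. No regression model, covariate, stratified estimate or adjusted sensitivity analysis is named. The section does not call the ratios unadjusted; it is silent.

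The secondary analysis in section 9.0 will "compare immunogenicity of the experimental 2-dose group in males with the immunogenicity of the 3-dose standard care group in females". This is at T3, with the same 0.5 limit for all nine types.

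The baseline data are there. Section 5.0 lists "Demographics (i.e., date of birth, age, ethnicity, race, marital status) and other information (i.e., height, weight, coverage, and clinic site" among the items collected. In section 4.0, "Study personnel will be required to enter information including the protocol number, the site number", followed by the participant's age and sex, before the assignment is issued. That section does not say whether any of these items stratifies the randomisation.

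**The concern.** There are two separate issues.

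- **Randomised aims (1, 2 and the within-sex parts of 3).** A baseline variable that predicts log titre, if left out of the analysis, leaves variance in the residual that could be removed at no cost. The rule fails an aim on any one of nine types, so interval width counts. If site or age stratify the randomisation, the analysis should also reflect them.
- **Secondary male-female comparison.** Participants are not randomised to sex. Section 4.0 recruits through pediatric, family medicine and women's health clinics, and through campuses, community venues and mailings. Women's health clinics supply females only, so age and site can differ by sex even though both share the 15–26 range. Body size can differ too. A formal non-inferiority conclusion would then rest on a ratio in which nothing controls for these differences.

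**Working it through.** **Inputs from section 9.0.** "The inferiority margin was set at 0.5"; true ratios "are equal to 1.2, with a standard deviation of 1.2 consistent with the power analyses conducted by a previous clinical trial"; one-sided α = 0.025; 91 evaluable per group for 90% power; 800 in total. The scale of the SD is not stated; I read it as the SD of natural-log titre.

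**The plan's own figure.** n = 2 × 1.2² × (1.960 + 1.282)² / (ln 2 + ln 1.2)² = 39.5, so 40 per group. The stated 91 does not reproduce. That is a separate matter. Below I take 91 as given, and also use 144: 800 split equally over four groups (my assumption) gives 200, and 200 × 0.85 × 0.85 = 144.5.

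**Precision in the randomised aims.** Adjustment multiplies the standard error by √(1 − R²). The documents give no R², so the values below are assumed. The interval half-width is t × 1.2 × √(2(1 − R²)/n), and the lowest observed ratio that passes is 0.5 × exp(half-width).

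| R² | CI narrower by | Lowest passing ratio, n = 91 | Power per type, n = 91, true ratio 1.0 | Same, true ratio 0.8 |
|---|---|---|---|---|
| 0 | – | 0.710 | 97.2% | 74.8% |
| 0.02 | 1.0% | 0.708 | 97.5% | 75.6% |
| 0.05 | 2.5% | 0.704 | 97.8% | 76.9% |
| 0.10 | 5.1% | 0.698 | 98.3% | 79.1% |

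In sample-size terms, 1/(1 − R²) − 1 gives a gain of 2% to 11%. With 144 per group, unadjusted power per type is 99.8% at a true ratio of 1.0 and 91.2% at 0.8.

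**What age alone could supply.** Assume that titres fall 3% or 5% per year and that ages are spread evenly over the 12 years of 15–26, so the SD of age is 12/√12 = 3.46 years.

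- 3% per year: slope −ln 0.97 = 0.0305; R² = (0.0305 × 3.46 / 1.2)² = 0.8%; CI narrower by 1 − √0.992 = 0.4%.
- 5% per year: slope −ln 0.95 = 0.0513; R² = (0.0513 × 3.46 / 1.2)² = 2.2%; CI narrower by 1 − √0.978 = 1.1%.

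An R² as high as 0.10 would therefore have to come mostly from other covariates.

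**Possible shift in the male-female ratio.** With a relative change b per year and a mean age difference of d years, the factor is (1 − b)^d or its inverse.

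- b = 0.01, d = 1: 0.99 or 1.01.
- b = 0.05, d = 3: 0.95³ = 0.857, or 1/0.857 = 1.166.

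The documents give neither b nor d, so this is an illustration only.

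**When such a shift would change the conclusion.** At 91 per group the lowest passing ratio is 0.710.

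- Inflation by 1.166 turns a fail into a pass only if the age-comparable observed ratio lies between 0.710/1.166 = 0.61 and 0.71.
- Deflation by 0.857 turns a pass into a fail only between 0.71 and 0.710/0.857 = 0.83.
- At 144 per group, where the lowest passing ratio is 0.660, the two ranges are 0.57 to 0.66 and 0.66 to 0.77.

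**The case against.** The case for leaving the plan alone is substantial. Sex already enters the analysis, because every primary comparison is made within sex. Under randomisation the within-sex raw ratio is a standard, valid estimate, so not adjusting is a choice and not an error. At a true ratio near 1 the gain hardly changes power. For the male-female comparison, eligibility is 15–26 in both sexes and no age imbalance is documented. Setting 2-dose males against the standard schedule in females is the stated purpose, and adjustment cannot separate sex from dose number. The comparison decides no primary hypothesis. All of this stands.

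Two replies limit it. First, the requirement that all nine types pass magnifies small gains when two doses are somewhat weaker. With 91 per group, a true ratio of 0.9 for every type and an assumed between-type correlation of 0.5, a normal approximation puts the chance that all nine pass at 64% unadjusted and 65% to 71% for R² of 0.02 to 0.10. Second, a shared eligibility range does not give equal ages within it, and the secondary comparison carries a formal decision rule.

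A reader might infer that age is an established driver of response in this trial. The background in section 1.0 does not show that: three doses remain recommended for older patients because 2-dose immunogenicity data are lacking. No relation between titre and age within 15–26 is given.

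A reader might also note that the analysis set depends on doses and sera falling within windows after randomisation, so balance within sex is not guaranteed. That is true, but it is a problem of the analysis set. Adjustment could reduce imbalance in measured factors; it would not cure the selection.

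**Conclusion.** The point holds in a limited form. For the randomised within-sex aims, the missing covariates cost a modest amount of precision: intervals wider by roughly 1% to 5% if R² is 0.02 to 0.10, and by about 0.4% to 1.1% from age alone under a slope of 3% to 5% per year. These figures rest on assumed R² values, an even age spread and an SD of 1.2 on the natural-log scale. The documents do not support reading this as bias in Aims 1 to 3, or as a threat to power under the plan's own assumptions.

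The more important part is the comparison of 2-dose males with 3-dose females. It is open to confounding by age, body size and site, in either direction, by an illustrative factor of up to 0.86 or 1.17 for age. It would be tempting to call that comparison confounded by age, or biased towards non-inferiority. Neither an age difference between the sexes nor its direction is documented, so only potential confounding can be claimed.

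**What to change.** Amend section 9.0 before any serology results are seen.

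- **Randomised aims.** For each type and sex, at T3 and T4, take the GMT ratio and its two-sided 95% CI from a linear model of log titre on arm, with age (continuous), site and any factor used to stratify the randomisation as covariates. Report the raw ratio as a sensitivity analysis. State in section 4.0 which factors, if any, stratify the randomisation.
- **Male-female comparison.** Report the ratio adjusted for age and for BMI derived from the recorded height and weight. Label it non-randomised. State that adjustment cannot separate sex from dose number and that differences by recruitment site may remain.

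No new data are needed. The cost is SAP wording and slightly more programming.
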